11 STUDY DISCONTINUATION

The study sponsor has the right to terminate this study at any time. Reasons for terminating the study may include, but are not limited to, the following:

- The incidence or severity of adverse events in this or other studies indicates a potential health hazard to subjects
- Subject enrollment is unsatisfactory
- Data recording is inaccurate or incomplete.

12 RECORD RETENTION

The investigator shall maintain all subject records for a period of two years after the latter of the conclusion or termination of the investigation or the time it is determined that the information is no longer needed to support a regulatory submission for market clearance.

The investigator must maintain accurate records of the receipt of all investigational material shipped by the sponsor, including the date and lot numbers received. In addition, accurate records must be kept on the amount and date that the investigational material, by lot number, was used and for each subject.

The investigator must assure that study supplies are used only in conjunction with subjects enrolled in the study and under the direct supervision of the investigator or co-investigators.

13 STUDY MONITORING REQUIREMENTS

It is the responsibility of the study Sponsor to ensure proper monitoring of the investigation and to see that all the clinical requirements are met. Either sponsor personnel or a contracted third party will perform monitoring. In general, monitoring will consist of an initiation visit to train the site on the proper use of the device and execution of the protocol. Ongoing monitoring will consist of periodic visits to the site to compare study eCRF data with site source data. The frequency of these visits will depend on site enrollment and observations during prior visits. During monitoring visits, the monitor may review the subject records to verify that all records and files are current and to assure compliance with all requirements of this protocol as well as with applicable IDE regulations. The final monitoring visit may also serve as the study close-out visit.

14 PROTOCOL DEVIATIONS/AMENDMENTS

An investigator may deviate from the protocol to protect the life or physical well-being of a subject in an emergency, and must notify the sponsor and the reviewing IRB within 5 working days after the emergency occurred. Except in such an emergency, an investigator may not deviate from the protocol

unless he/she obtains the prior approval of the sponsor. Depending on the specifics of the deviation, IRB approval may also be required.

15 DEVICE ACCOUNTABILITY

All investigational devices will be tracked during the study by either lot number or serial number depending on the device. The Sponsor will track all device shipments and all device returns. An accountability log will be maintained at each site to record the date and number of devices received by the site as well as the date and number of devices used, returned to the Sponsor, and/or disposed of during the study. This log will be included in the review of documentation during monitoring visits. Overall accountability for all devices will be maintained by the Sponsor.

APPENDIX A: STUDY ASSESSMENTS

All subjects shall be assessed according to the following schedule unless otherwise specified:

Assessment	Screening	Pre-Treatment (Baseline)	Treatment	Post-Treatment	Day 1	Week 2	Week 4
Treatment Window	Day -7 to Day 0	Day 0	Day 0	Day 0	Day +1	Days 10-16	Days 21-35
Informed Consent	x						
Demographics/Medical/Ocular history	x						
Concomitant Systemic and Ophthalmic Meds	x						x
Discomfort and Pain Questionnaires		x		x	x	x	x
OSDI		x				x	x
Uncorrected Visual Acuity		x		x	x	x	x
Keratometry		x				x	x
Manifest Refraction		x				x	x
BSCVA		x		x	x	x	x
Slit Lamp for Anterior Segment Health		x		x	x	x	x
Lid Margin Abnormalities		x		x	x	x	x
Eyelid Margin Assessment		x		x*	x	x	x
Tear Break-Up Time		x				x	x
Corneal Fluorescein Staining Slit Lamp Evaluation		x		x	x	x	x
Meibomian Gland Assessment and Scoring (assess by a masked rater)		x				x	x
Intraocular Pressure		x		x		x	x
iLux OR LipiFlow Treatment per IFU/User Manual			x				
Adverse Events			x	x*	x	x	x

* 1 hour post-treatment

**APPENDIX B: OCULAR SURFACE DISEASE INDEX (OSDI)
QUESTIONNAIRE**

APPENDIX C: DISCOMFORT AND PAIN QUESTIONNAIRES

To be asked at Baseline

Place a vertical line on the following scales at the point that indicates the discomfort in or around your eyelids, or face over the past week. Discomfort includes feelings of pressure, tightness, heaviness, burning, and other negative sensations.

To be asked immediately post-procedure:

Place a vertical line on the following scales at the point that indicates the discomfort in or around your eyelids, or face during the procedure. Discomfort includes feelings of pressure, tightness, heaviness, burning, and other negative sensations.

[figure not shown]
To be asked at 2 weeks & 4 weeks:

Place a vertical line on the following scales at the point that indicates the discomfort in or around your eyelids, or face over the past week. Discomfort includes feelings of pressure, tightness, heaviness, burning, and other negative sensations.

[figure not shown]
To what degree do you feel the discomfort is due to the treatment you received as part of this study:

- 1) Entirely due
- 2) Partially due
- 3) Not due

Right Eye

Left Eye

To be asked at Baseline

Using the faces below as a guideline, place a vertical line on the following scales at the point that indicates the intensity of pain in or around your eyelids, or face over the past week.

To be asked immediately post-procedure:

Using the faces below as a guideline, place a vertical line on the following scales at the point that indicates the intensity of pain in or around your eyelids, or face during the procedure.

To be asked at 2 weeks & 4 weeks:

Using the faces below as a guideline, place a vertical line on the following scales at the point that indicates the intensity of pain in or around your eyelids, or face over the past week.

[figure not shown]
To what degree do you feel the discomfort is due to the treatment you received as part of this study:

- 1) Entirely due
- 2) Partially due
- 3) Not due

[figure not shown]

Pain Scale

Right Eye

Left Eye

APPENDIX D: ADVERSE EVENT DEFINITIONS

Adverse Event (AE)	
Any untoward and unintended sign, symptom or disease temporally associated with the use of an investigational drug or device, or other protocol-imposed intervention, regardless of the suspected cause
 
 • Chronic but stable conditions or diseases are not AEs • Changes in a chronic condition or disease consistent with natural disease progression are not AEs
Serious Adverse Event (SAE)	
SAEs are AEs that:
 
 • Led to death • Led to serious deterioration in the health of the patient that resulted in: 
 ○ A life-threatening illness or injury ○ A permanent impairment of a body function ○ In-patient or prolonged hospitalization ○ Medical or surgical intervention to prevent life-threatening illness or injury or permanent impairment to body structure or a body function
AE Severity	
Mild: Awareness of sign or symptom, but easily tolerated Moderate: Discomfort enough to cause interference with usual activity Severe: Incapacitating with inability to work or do usual activity
 
 • Severity is irrespective of procedure relationship or seriousness of the event • Severity is a measurement of intensity but not seriousness; thus, a severe reaction is not necessarily a SAE
AE Expectedness	
Anticipated: The nature, severity, or degree of incidence was previously described, including those anticipated events listed in the protocol and/or IFU/User Manual of the device. Unanticipated: The nature, severity, or degree of incidence was not previously described.

AE Relatedness	
Not related: Clearly related to other factors such as subject’s clinical state, therapeutic interventions, concomitant disease or therapy administered to the subject, and does not follow a known response pattern to the procedure Related: Follows a reasonable, temporal sequence from the time of procedure and/or follows a known response pattern to the study procedure and cannot be reasonably explained by other factors such as subject’s clinical state, therapeutic interventions, or concomitant therapy administered to the subject

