2 INTRODUCTION

Meibomian glands are located in the tarsal plate of the upper and lower eyelids, where they terminate along the interior rim (or margin) of the eyelids. These glands secrete meibum, which is a lipid-rich essential component of a healthy tear film. When sufficient meibum is not present in the tear film, the aqueous layer of the tear film is disrupted and readily evaporates causing irritation, redness, and inflammation of the lid margin and surrounding tissues. Meibomian Gland Dysfunction (MGD) is associated with a failure of these glands to produce adequate quantities of meibum due to atrophy, inflammation, or obstruction, and is thought to be the most common cause of evaporative dry eye disease [1].

A common clinical treatment to restore normal gland function in patients with obstructive MGD involves the application of heat and pressure therapy to the eyelids to express the meibomian gland obstruction and other material from the gland [2]. Warming the eyelid tissue softens or melts the meibum, which is known to facilitate expression using pressure.

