7.2.5 Safety Endpoints

The primary safety endpoint is the comparison of the incidence of device-related adverse events (e.g., changes in the lid margin, development of floppy eyelids, entropion or ectropion; and lash integrity) for the two treatments. The reporting period is from baseline through the last study visit.

The secondary safety endpoint is the evaluation of discomfort and pain during treatment and changes from baseline following treatment for the test and control devices for the following assessments:

- Ocular Surface Staining
- Intraocular Pressure
- BSCVA

Adverse events and other findings shall be summarized by presenting the percentages of subjects with each event type. Continuous endpoints shall be summarized using summary statistics such as means, medians, standard deviations, minima, maxima, and relevant percentiles. Definitions of adverse events, serious adverse events, and categorizations of events can be found in Appendix D.

All adverse events shall be evaluated beginning with onset, and evaluation shall continue until resolution is noted, or until the investigator determines that the subject's condition is stable.

All AEs shall be characterized by the following criteria (see Adverse Event Definitions in Appendix D):

- Event diagnosis
- Intensity or severity (*mild, moderate, severe*)
- Expectedness (anticipated, unanticipated)
- Relatedness to study treatment (*related, not related*)
- Treatment (none, medication, non-drug treatment/procedure, ER visit/hospitalization)
- Action taken (none, study procedure interrupted, study procedure discontinued)
- Outcome (resolved without sequelae, resolved with sequelae-specify, ongoing at time of assessment, death, unknown)

If more than one distinct adverse event occurs, each event shall be recorded separately.

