7.2.5.1 Anticipated Adverse Events

- Eyelid/eye Pain
- Eyelid Irritation or Inflammation
- Ocular Surface Irritation or Inflammation
- Ocular Symptoms – Burning, stinging, tearing, itching, discharge, redness, foreign body sensation, visual disturbance, sensitivity to light.

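### Appendix D's two relatedness definitions do not give every adverse event exactly one code, so discretion in coding symptom events can shift the device-related rates compared as the primary safety endpoint

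*Combined protocol and SAP*

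**What the plan says.** **Endpoint.** Section 7.2.5 states: "The primary safety endpoint is the comparison of the incidence of device-related adverse events". Section 4.4.3 says the same. The examples given in both places are lid-margin changes, floppy eyelids, entropion, ectropion and lash integrity. No test, interval, margin or success rule is attached.

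**Codes.** Section 7.2.5 lists two values for relatedness: related and not related. There is no intermediate or undetermined level.

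**Definitions (Appendix D).** 'Not related' requires that the event is clearly due to other factors "and does not follow a known response pattern to the procedure". 'Related' requires a reasonable temporal sequence and/or that the event "follows a known response pattern to the study procedure and cannot be reasonably explained by other factors". The subject's clinical state is named among the factors in the closing clause, "cannot be reasonably explained by other factors".

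**Overlap with the disease.** Section 7.2.5.1 lists as anticipated ocular symptoms: "Burning, stinging, tearing, itching, discharge, redness, foreign body sensation, visual disturbance, sensitivity to light". Section 2 says of the disease that the tear film "readily evaporates causing irritation, redness, and inflammation of the lid margin and surrounding tissues". Section 5.1 requires an OSDI score of at least 23 at baseline.

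**Masking.** Section 4.2 calls the trial open-label. Sections 4.4.1 and 6.4 (Table 1) require masking of the MGS rater only. Section 9 has the Medical Monitor receive accounts of adverse events. No masked adjudication of relatedness, default code or tie-break rule is given.

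**The concern.** With two codes, the definitions should give every adverse event exactly one. These do not. The exposed case is a new or worsened symptom, such as burning or redness after treatment, that is on the anticipated list and could also reasonably be the dry eye with which every subject enters. The known pattern rules out 'Not related'; on the natural reading, the other explanation rules out 'Related'. Whoever codes the event must still choose.

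That choice enters the numerator of the primary safety endpoint. If the coder knows the device, the choice can differ by arm. The compared rates could then separate without a true difference, or a true difference could be hidden. Section 4.2 gives the goal as verifying that technological differences between the devices do not adversely affect safety, so this comparison matters.

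**Working it through.** **1. Plan's own figures.** The plan gives no event rate or power for safety, so there is nothing to reproduce on this point. Only the arm size is needed: 128 subjects randomized 1:1 (section 4.2) is 128/2 = 64 per arm. As a check, a two-sample non-inferiority t-test with 64 per arm, margin 5, SD 8 and one-sided alpha 0.025 (stated in section 7.2.4 for the secondary endpoint, assumed here for the co-primaries) gives 93.9% power, as section 7.2.4 states.

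**2. The definitions as logic.** Each event has three attributes: reasonable timing (yes/no), known pattern (yes/no) and other cause (none, reasonable, clear). That makes 2 × 2 × 3 = 12 combinations.

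- 'Not related' = other cause clear AND no known pattern.
- 'Related', reading A (natural) = (timing OR pattern) AND no other reasonable cause.
- 'Related', reading B = timing OR (pattern AND no other reasonable cause).

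| # | Timing | Pattern | Other cause | Code, reading A | Code, reading B |
|---|---|---|---|---|---|
| 1 | yes | yes | none | related | related |
| 2 | yes | yes | reasonable | neither | related |
| 3 | yes | yes | clear | neither | related |
| 4 | yes | no | none | related | related |
| 5 | yes | no | reasonable | neither | related |
| 6 | yes | no | clear | not related | both |
| 7 | no | yes | none | related | related |
| 8 | no | yes | reasonable | neither | neither |
| 9 | no | yes | clear | neither | neither |
| 10 | no | no | none | neither | neither |
| 11 | no | no | reasonable | neither | neither |
| 12 | no | no | clear | not related | not related |

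Reading A leaves 7 of 12 without a code, including all four with a known pattern and a reasonable or clear other cause (rows 2, 3, 8, 9). Reading B leaves 4 of 12 without a code and gives row 6 both. Neither reading classifies every event exactly once. Rows 2, 3 and 5 change from no code to 'Related' with the parsing alone.

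These are counts of logical cases, not of expected events.

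**3. Possible effect on the rates (all event counts assumed).** Take 64 per arm, 3 subjects per arm with a clear device event and g per arm with an ambiguous event only, so there is no true difference. Reported incidence = (3 + number of ambiguous events coded related)/64.

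| g per arm | Ambiguous coded related, arm 1 vs arm 2 | Incidence | Fisher p |
|---|---|---|---|
| 3 | 0 vs 3 | 3/64 = 4.7% vs 6/64 = 9.4% | 0.49 |
| 6 | 0 vs 6 | 3/64 = 4.7% vs 9/64 = 14.1% | 0.13 |
| 10 | 2 vs 8 | 5/64 = 7.8% vs 11/64 = 17.2% | 0.18 |
| 10 | 0 vs 10 | 3/64 = 4.7% vs 13/64 = 20.3% | 0.014 |

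The p-values only give scale, since the plan specifies no safety test. Of these four cases only the extreme one, with all ten ambiguous events coded one way in one arm and the other way in the other, falls below 0.05.

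**The case against.** **Much dry-eye symptomatology never reaches this step.** Appendix D excludes stable chronic conditions and changes consistent with natural progression from adverse events. That stands. A reader might infer that the ambiguous event is the typical one, or the largest class. The documents give no frequencies and do not support that. What remains is the new or worsened symptom. The exclusion is itself a judgement made before relatedness is coded.

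**The gap depends on parsing.** Under reading B a known-pattern symptom with reasonable timing is 'Related'. Because Appendix D defines an adverse event as temporally associated with the intervention, rows without timing may be rare. Keeping only rows 1 to 6, reading B leaves none uncoded and one coded both ways; reading A still leaves 3 of 6 uncoded. This is a fair limit, but the text does not say which reading applies.

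**The named events are mainly structural.** Entropion and ectropion affecting lid function are excluded at entry (section 5.2, item 11), and the eyelid margin is assessed at baseline and at every later assessment point (Appendix A). These events are hard to attribute to dry eye. That stands for entropion, ectropion, floppy eyelids and lash integrity. Lid-margin changes are more exposed, because section 2 describes lid-margin inflammation as part of the disease.

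**Other data bypass attribution.** Section 7.2.5 summarizes events by type without limiting this to related ones, and pain, discomfort, staining, IOP, BSCVA and OSDI are recorded separately. This helps, but none of it is a stated between-arm comparison of all ocular adverse events, and it does not repair the endpoint's numerator. The subject's own three-level attribution question in Appendix C is not linked to relatedness coding.

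**The coder is not named.** That the coder knows the arm is an inference from the open-label design and the absence of stated masking outside the MGS.

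**Conclusion.** The point holds as a defect in the definitions. They are neither exhaustive nor unambiguous, and they feed the numerator of the primary safety endpoint in an open-label trial with no stated default or masked adjudication. The exposed events are new or worsened ocular symptoms and, to a lesser degree, lid-margin changes; the structural events are less exposed.

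A reader might go further and infer that coding decides the safety endpoint. The documents do not support that: no safety test, margin or success rule exists, so no formal conclusion flips. What can move is the pair of rates being compared. The size of the shift is unknown. Under the assumed counts, fully differential coding moves the difference by 3/64 = 4.7 points (g = 3) to 10/64 = 15.6 points (g = 10); coding applied alike in both arms moves only the level. The conclusion rests on the wording of Appendix D and section 7.2.5, and on the inference that relatedness is coded with knowledge of the arm.

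**What to change.** **Appendix D.** Keep 'Not related' as it stands, with both conditions: clearly due to other factors, and not following a known response pattern. Define 'Related' as every other adverse event. In the table above, rows 6 and 12 are then 'Not related' and the other ten are 'Related', so each event has exactly one code and the parsing question disappears.

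The pattern condition should stay. If a clear other cause were enough by itself, an event fitting the device's known pattern could be coded not related, which the current text forbids.

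**Section 7.2.5.** Beside the device-related comparison, add a between-arm comparison of all ocular adverse events regardless of relatedness. The new definition does not mask the coder, and judging that a cause is clear remains discretionary. The added comparison does not depend on that judgement.

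**Cost.** A change to the protocol and CRF-guideline wording, and one more table; no added visits, subjects or staff. Reported device-related rates may rise in both arms. In the assumed example with ten ambiguous events per arm, consistent application gives 13/64 = 20.3% in each arm, with no spurious difference.
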